 be evenly divided over countries and conditions (10 ImRs and 10 EMDR participants in the
- be evenly divided over countries and conditions (10 ImRs and 10 EMDR participants in the
 Netherlands, 10 ImRs and 10 EMDR participants in Australia). Furthermore, sampling will be driver
- Netherlands, 10 ImRs and 10 EMDR participants in Australia). Furthermore, sampling will be driven
 by maximization of diversity (age, gender, socio-economic status, ethnicity, etc.) following the
- 630 methodological standards of qualitative research.
- 631
- 632 **4.2 Inclusion criteria (see study protocol)**
- 633634 **4.3 Exclusion criteria (see study protocol)**
- 635636 5. Intervention: (see study protocol)
- 637

638 6. Primary study parameters/ outcome of the study:

- 639 Effective elements of followed treatments according to patients
- 640
- 641 **7. Secondary study parameters/ outcome of the study:**
- 642 Not applicable
- 643

8. Nature and extent of the burden and risks associated with participation, benefit and grouprelatedness:

- 646 The burden for patients exists of time for the interview of one hour.
- 647

648 **9.** Dissemination and Implementation.

- 649 The results of the study will be disseminated in the scientific community by a publication in a
- 650 scientific journal and presentations at scientific conferences.

652 **10. Time schedule**

- 653 June 2016: start of qualitative interviews.
- 654 September 2017: last treatments finish.
- 655 November 2017: last interviews held.
- 656 September 2017- September 2018: analysing the transcripts of the interviews, reports of results
- 657 (article, conferences).
- 658

- 659 Appendix 3. Study protocol of substudy 3: change in schema modes along PTSD treatment as index
- 660 for change in personality problems.
- 661
- 662 Local research team GGZ-NHN
- 663 [name] (Manager Trauma Department GGZ-NHN)
- 664 [name] (Manager Research Department GGZ-NHN)
- 665 [name] (researcher)
- 666 [name] (researcher)
- 667 [name] (research assistant)
- 668 669

670 **1. Introduction**

Child maltreatment is not only related to the development of PTSD (Ullman & Brecklin, 2002) but
also to the development of personality pathology (Johnson et al., 2006, Lobbesteal et al., 2010).
Many patients diagnosed with childhood-trauma related PTSD also suffer from comorbid personality
pathology (Johnson et al., 2000). Difficulties in emotion regulation and interpersonal functioning are
problems in PTSD as well as personality disorders. These problems substantially decrease the level of
healthy functioning of patients in all life domains (Briere, Hodges, & Godbout, 2010; MacIntosh,
Godbout & Dubash, 2015).

678

679 There are various evidence-based treatments for PTSD, and several have shown to be effective for 680 childhood-trauma related PTSD (Ehring et al., 2014). The studies on PTSD and childhood-trauma 681 related PTSD mainly focussed on the effects on PTSD symptoms. Very little is known about the 682 effects on comorbid personality pathology. Some evidence is found for the reduction of emotion 683 regulation problems and for improvements in interpersonal problems (Cloitre et al., 2010), anger 684 control, externalisation of anger and hostility (Arntz, Tiesema & Kindt, 2007). One study examined 685 the impact of PTSD treatment on comorbid personality disorders, and found significant reduction of 686 the axis II pathology (Markowitz et al., 2015).

687 Another approach to personality pathology is the Schema Mode concept stemming from Schema

688 Therapy. Schema modes reflect the emotional and cognitive states and coping responses that are

- active at a given time. Modes can be adaptive or maladaptive: the stronger the pathology of a
- 690 patient, the more the number and intensity of the maladaptive modes (Young et al., 2003).

691 Investigating the effect of the PTSD treatment on Schema Modes can offer a different and additional

- 692 insight in the effects of the PTSD treatment on comorbid personality pathology. To the best of our
- 693 knowledge no research has yet been done on the effects of PTSD treatment on Schema Modes.
- 694

696 **2.** Aim

697 In this study we want to investigate the effectiveness of ImRs and EMDR on comorbid Schema 698 Modes. Both interventions are applied in the treatment of PTSD as well as in the treatment of 699 personality pathology (Arntz, 2015, Mosquera, Leeds, & Gonzalez, 2014). It is hypothesised that ImRs 700 is more effective than EMDR in the reduction of dysfunctional Modes and the enhancement of the 701 adaptive Modes. The main reason for this hypotheses is that ImRs is more directly aimed at 702 modelling effective coping skills by the therapist in interpersonal relations, and encouraging patients 703 to actively perform these skills. Therefore, the development of active coping of the client and of 704 change of the meaning of the trauma-events is established. EMDR on the other hand is more aimed 705 at the weakening of the sensory aspects of the trauma memory (Engelhard et al., 2010, 2011; see van 706 den Hout & Engelhard, 2012). In addition, this study might provide insight into the correspondence 707 between PTSD, Schema Modes and the PTSD treatment outcome. 708 709 Research question 710 Main: Is ImRs more effective than EMDR in the reduction of dysfunctional schema modes and the 711 enhancement of the functional modes within patients suffering from childhood-trauma related 712 PTSD? 713 Optional: To what extent is the severity of Schema Modes at baseline predictive for treatment 714 outcome on PTSD symptoms? Is there a correlation between the efficacy of the PTSD treatment on 715 Schema Modes and on PTSD symptoms? 716 717 Objective 718 To enlarge our knowledge of the effect of ImRs and EMDR on Schema modes. With this knowledge, 719 we can improve treatment indications for patients suffering both from childhood-trauma related 720 PTSD and dysfunctional Schema Modes. 721 722 3. Study design 723 Design 724 This is an additional research question within the multi-centre Randomized Clinical Trial on the 725 effectiveness of ImRs vs EMDR as treatment of childhood-trauma related PTSD in adults. 726 727 In the main protocol, there are six to seven assessments within this study (see schedule below). In 728 this additional study the Schema Modes Inventory (SMI) will be added at baseline, post-test and 8 729 weeks after baseline follow-up.

Assessments	Instruments
If applicable;	CAPS, IES-R
Start Naturalistic wait	
Baseline	CAPS, IES-R, SMI
After 6 sessions	CAPS, IES-R
After 12 sessions	CAPS, IES-R
Posttest	CAPS, IES-R, SMI
Follow-up (8 weeks after postest)	CAPS, IES-R, SMI
Follow-up (one year after baseline)	CAPS, IES-R

731 Participating sites: GGZ-NNH, RIAGG Maastricht, Buro van Roosmalen (Roermond/Venlo/Venray),

732 PsyQ departments Amsterdam & Beverwijk, Sinaï Centrum Amstelveen & Amersfoort,

733 Universitätsklinikum Schleswig-Holstein, Lübeck, Germany, and Perth, Australia.

- 734
- 735 Procedure
- 736 Follows the study protocol of IREM.
- 737
- 738 Data-analysis
- 739 Mixed regression analysis.

740

741 **4. Study population**

742 The in- and exclusion criteria and sample size calculation (N=142) are in line with the study protocol

- of IREM.
- 744
- 745 **5. Intervention**
- 746 Imagery Rescripting (ImRs) versus Eye Movement Desensitization and Reprocessing (EMDR).
- 747
- 748 6. Main study parameter
- 749 Schema Modes: Schema Mode Inventory (SMI).
- 750 The SMI has been derived from the Schema Mode Inventory (long version, 270 items). The list
- consists of 118 items, which can be scored on a six-point Likert-type scale ranging from 1 (never or
- almost never) to 6 (always) (Young et al., 2003).

753	There are English, Dutch and German versions, the last two are both validated and the results	
754	indicated a 14-factor structure and acceptable to good psychometric properties (Lobbestael et al.,	
755	2010, Reiss et al., 2012).	
756		
757	The SMI is a self-report questionnaire that measures 14 Modes:	
758	- Vulnerable Child, Angry Child, Enraged Child, Impulsive Child and Undisciplined Child (domain	
759	1: Maladaptive Child Modes);	
760	- Compliant Surrender, Detached Protector, Detached Self-Soother, Self-Aggrandizer and Bully	
761	and Attack (domain 2: Coping Modes);	
762	- Punitive Parent and Demanding Parent (domain 3: Parent Modes);	
763	- Healthy Adult and Happy Child (domain 4: Healthy Modes).	
764		
765	Administration time is estimated at 20 minutes (Lobbestael, 2010).	
766		
767	7. Secondary study parameter	
768	PTSD symptoms: IES-R, CAPS	
769		
770	8. References	
771	Arntz, Arnoud. (2015). Imagery rescripting for personality disorders Healing early maladaptive	
772	schemas. [References]. In: Thoma, Nathan C [Ed]; McKay, Dean [Ed]. (2015). Working with emotion in	
773	cognitive-behavioral therapy: Techniques for clinical practice. (pp. 175-202). xv, 416 pp. New York,	
774	NY, US: Guilford Press; US.	
775		

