453 Appendix 1. Study protocol of substudy 1: Remembering what happens: consistency and accuracy 454 of memory for repeated traumatic events

455

456 Investigator: [name], Royal Holloway University.

- 457 Co-investigators: [name], [name], [name], [name]
- 458
- 459 Introduction.
- 460

461 Accuracy and validity of memories of for instance traumas is often based on data indicating 462 consistency. However, research has found that consistency is not always a good indicator of accuracy 463 (see Fisher et al., 2013 for a review). The present project aims at investigating whether this 464 counterintuitive finding can be extended to those individuals who experienced multiple instances of 465 abuse. Importantly, what we know from the memory literature on repeated events is almost 466 exclusively based on studies of memory for single events in children, created in a laboratory 467 environment. The study will investigate memories of adults for repeated traumatic events in 468 participants' real lives on consistency, and compare these to memories of non-traumatic events.

469

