504 To summarise so far, a review of theory and research with child witnesses as well as case studies of 505 alleged child victims leads us to expect recall of repeated events to rely on a mixture of specific and 506 general event representations, which would be in line with both schema and fuzzy trace theory. 507 Contrary to what one might expect, the literature also suggests obtaining a generic description first 508 may facilitate recall of episodic content (Connolly & Gordon, in press; see Brubacher & LaRooy, 2013 509 for a case study). Turning to the credibility of memories for repeated events, once again we could 510 only find evidence in the literature on children's memories, despite of a thorough search in several 511 databases. Connolly et al. (2008) made adult participants watch video recordings of children 512 describing an event. For half of the children, the event had been experienced once and for half of the 513 children the event was the last in a series of similar events. All children were similarly accurate; 514 however, repeat event children were judged to be less credible than the single-event children. An 515 analysis of the content of the reports revealed that most of the variability in credibility ratings could 516 be attributed to differences in consistency. 517 518 Hypotheses.

Accounts provided by patients who have been multiply traumatised compared to those with a single trauma, and by patients with more severe symptoms, will show an increased reliance on generic rather than event-specific information, and increased inconsistency in their reports. We predict similar findings with neutral memories but less fragmented accounts than in the traumatic memories.

525 Method.

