526 The researcher will record whether the individual has suffered a single or repeated trauma and 527 meets diagnostic criteria for PTSD in accordance with DSM-5. No personal data will be recorded 528 other than patient age, gender, type of and age at trauma, and scores on the screening measures 529 that are being administered as part of the RCT. A narrative memory report will be elicited at baseline 530 before the patient begins therapy and again six weeks' post-treatment. All patients will be using a PC 531 to write an account of the index trauma and where there are multiple traumas to describe the one 532 they have the clearest memory of. We will also elicit control accounts describing a neutral single or 533 repeated event such as a day trip to a novel location (SE) or the birthday that is the clearest to them 534 (RE). The Dutch interview data will be coded in Dutch using native Dutch speakers; sim. for German 535 interviews. Narratives will also be coded for coherence by dividing them into utterance units, defined 536 as clauses with a single thought, idea or action (see Jones et al., 2007). There are many 537 autobiographical memory studies showing similar linguistic features in English and Dutch studies 538 (e.g., Hermans et al., 2008). 539 Patients will complete the tasks for the memory substudy during screening and post-treatment 540 assessment sessions of the RCT. All patients will be completing tasks individually on a PC. As part of 541 the study participants are instructed to describe their clearest memory for the index trauma. This is 542 the childhood event (before the age of 16) for which they will receive treatment. The memories will 543 be typed into a PC by the patient during baseline data collection prior to the trial and once again 6-7 544 weeks later when they have completed the treatment phase of 12 sessions. The patients will also 545 complete a control task where they give an account of a single or repeated event (for example, a 546 birthday versus a visit to a novel location). It will be recorded whether the index trauma is a single or 547 multiple event.

548 Appendix 2. Study protocol of the qualitative study.

549

550 Working title substudy: Patients' perspective on the effective working mechanisms in ImRs and

551 **EMDR; a qualitative study of patients' perspectives** 552

553 **Researchers**:

- 554 Drs. [name], GZ-psycholoog i.o. tot Klinische Psycholoog (PsyQ)

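### In the memory substudy the neutral account has no age limit and its event age is not listed, so a trauma-versus-neutral difference in fragmentation could reflect memory age

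*Protocol*

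**What the plan says.** Protocol Appendix 1, Method, ties the trauma account to "the childhood event (before the age of 16) for which they will receive treatment". Section 4.2 admits patients aged 18 to 70.

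Each patient also writes a neutral control account, of a single or "repeated event such as a day trip to a novel location (SE) or the birthday that is the clearest to them". A later paragraph of the same Method section repeats that patients "complete a control task where they give an account of a single or repeated event (for example, a" birthday or a trip somewhere new. Neither description gives an age, date or period of life, and neither asks the patient to match the neutral event to the trauma.

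On data, the Method states "No personal data will be recorded" and then names the exceptions: "other than patient age, gender, type of and age at trauma, and scores on the screening measures". Age at the trauma is listed; age at the neutral event is not.

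The comparison is intended. The Introduction to Appendix 1 says the study will take trauma memories and "compare these to memories of non-traumatic events". The Hypotheses add: "We predict similar findings with neutral memories but less fragmented accounts than in the traumatic memories".

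**The concern.** A control account should differ from the trauma account in its content and in little else. Here the two can also differ in how old the memory is and in how old the person was when the event happened. Both are restricted for the trauma account (an event in childhood, years ago) and left open for the neutral account (anything from last month to early childhood).

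Appendix 1 gives reasons to think both matter. Its Introduction holds that exact detail fades quickly and that this hampers access to particular instances. It also reports that children supply more episodic detail as they get older. If patients tend to choose neutral events that are more recent, or from adult life, the neutral accounts may look more coherent whether or not trauma has any effect of its own. That is the direction the substudy predicts. At stake is the interpretation of one stated hypothesis: whether poorer coherence is specific to trauma.

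**Working it through.** **Figures in the plan.** The substudy states no sample size or effect size. The parent trial's N = 128 (Section 4.4: d = 0.5, 80% power, two-sided 0.05) reproduces: the two-sample t-test needs 63.8, so 64 per arm, with power 0.801. Allowing for 10% dropout gives 128/0.9 = 142.2, against 142 stated. These figures are not in dispute. N = 128 serves below only as a plausible number of pairs.

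**Age of the trauma memory.** The event precedes age 16, so time since the event exceeds current age minus 16:

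| Current age | Trauma memory is older than |
|---|---|
| 18 | 2 years |
| 30 | 14 years |
| 40 | 24 years |
| 70 | 54 years |

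The neutral memory has no lower bound. The gap between the two is uncontrolled and can reach decades.

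**What one extra data item would supply.** For a patient of current age A, with age a_T at the trauma and a_N at the neutral event, the difference in time since the event is (A − a_T) − (A − a_N) = a_N − a_T. Within a patient, then, the gap in memory age equals the gap in age at the event. A and a_T are on the list of recorded data; a_N is the only missing term.

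**What a shift would do, under assumptions.** Suppose there is no trauma effect, but memory age moves the trauma-versus-neutral difference by d standard deviations (equal SD for both account types). Let r be the correlation between a patient's two scores. The paired effect is d_z = d/√(2(1 − r)), and the noncentrality is d_z√N on N − 1 degrees of freedom. For d = 0.2 and N = 128:

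- r = 0.3: d_z = 0.2/√1.4 = 0.169, noncentrality 1.91, P(p<.05) = 0.475.
- r = 0.5: d_z = 0.2/√1 = 0.200, noncentrality 2.26, P(p<.05) = 0.612.

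| Assumed shift d | r = 0.3 | r = 0.5 |
|---|---|---|
| 0 | 0.050 | 0.050 |
| 0.1 | 0.158 | 0.202 |
| 0.2 | 0.475 | 0.612 |
| 0.3 | 0.812 | 0.920 |
| 0.5 | 0.997 | 1.000 |

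The values of d and r and the number of pairs are all assumptions. The table shows how sensitive a paired test is to a modest shift. It does not estimate the shift.

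**The case against.** The strongest reply is that this is peripheral and of unknown size. It touches half a sentence of an adjacent substudy's hypotheses. Section 8.1 gives the substudy's purpose as single versus repeated trauma and does not mention neutral accounts. Nothing shows that patients will choose recent events; a childhood birthday is allowed. Fading of detail is not the same as fragmentation, fast fading may level off early, and re-experiencing in PTSD means that ordinary forgetting cannot be assumed for trauma memories. All of this stands, and it limits the point to one prediction with a bias that cannot be quantified.

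Three stronger readings are tempting and are not supported:

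- *That the problem cannot be repaired afterwards.* The data clause limits personal data and is not clearly a complete list of variables: the same paragraph also records single or repeated trauma and diagnostic status, which the list does not name. Age at the neutral event could be asked later, or coded from the narrative where it shows.
- *That a positive result would say nothing about trauma.* The documents support only that trauma could not be separated from memory age as the explanation.
- *That the neutral single-versus-repeated contrast is itself confounded with patient group, or spoiled because only the birthday is chosen for clarity.* The protocol does not say how the type of neutral event is assigned. The clearest-instance rule mirrors the instruction for multiple traumas, and the trip and birthday are offered as examples.

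What the reply does not remove is that the plan as written neither matches the events nor lists the item needed to adjust for the mismatch. An analysis plan could name a covariate but could not supply an item that nobody collects.

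**Conclusion.** The point holds in a limited form. As Appendix 1 is written, a finding that neutral accounts are less fragmented could not be attributed to trauma rather than to the age of the memory or the patient's age at the event. This rests on the text of the Method and Hypotheses. It needs no assumption about which events patients actually choose, only that the choice is unrestricted and its age is not listed.

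The size of the bias is unknown. The false-positive rates above are conditional on assumed shifts and correlations and should not be read as predictions.

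The comparison of single with repeated trauma and the trial's CAPS endpoint at 8 weeks are not affected. The matter is worth correcting for the substudy and has no bearing on the main trial result.

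**What to change.** In Appendix 1, Method:

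1. Ask for a neutral event from childhood, before age 16 and as near as feasible to the patient's age at the index trauma.
2. Add age at the neutral event to the recorded data, for every account. For accounts already collected, ask the patient retrospectively or code it from the narrative.
3. Include time since the event as a covariate in the trauma-versus-neutral comparison, and interpret that comparison cautiously where memory ages do not overlap. Every trauma precedes age 16, so if most neutral events come from adult life the adjustment relies on extrapolation. Recording the age is therefore weaker than matching.

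The cost is a line of instruction and one data field. The main downside is that some patients may find a neutral childhood event harder to recall. The protocol is dated April 2016 and Section 10 has the last treatments finishing in September 2018, so on that schedule later accounts could still be collected under the revised instruction.

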- 852 The last years there has been done a lot of research of the underlying mechanisms of ImRs. One 853 explanation of ImRs is that it helps the patient to express inhibited action tendencies and get unmet 854 needs met (Arntz, 2012).
- 855

856 Hypothesis: As more inhibited action tendencies are being expressed and unmet needs of safety are 857 met, the PTSD symptoms will decrease in patients with early childhood trauma.

858

859 860 2. Aim

861 To clarify the working mechanisms of the ImRs protocol, in order to enlarge the chance of a 862 successful treatment of PTSD-symptoms with clients with early childhood trauma.

863 864 3. Study design

865 The study is a multi-centre Randomized Clinical Trial (RCT). There are five or six assessments: at start 866 of wait (if applicable), just before treatment, halfway treatment, after treatment, 8 weeks after 867 treatment, and at 1-year follow-up. At participating sites there usually is a naturalistic wait of 868 approximately 6 weeks (estimated mean). To assess changes due to time only, assessments take 869 place before and after wait. In case there is no naturalistic wait before treatment can start, the pre-870 wait assessment will be skipped.

- 871 At start of every session a self-report of PTSD symptoms will be taken to explore whether treatments 872 differ in their speed of improvement in the three symptom clusters of PTSD.
- 873 874 Substudy
- 875 All sessions will be audio recorded. Recordings will be destroyed 5 years after publication of the main 876 findings. Non-drawn recordings will be destroyed immediately.
- 877

- 878 The records of ImRs will be rated by 2 independent trained judges on: 879
 - 1. The expression of inhibited action tendencies
 - 2. Get unmet needs met.
- 881 882 Uitwerking
- 883 What are inhibited action tendencies?
- 884 885 Emotion Action tendency 886 Helplessness, fear Attack the other and defend oneself

887 888	Helplessness, anger	Attack the other, to put the other in his place, to destroy the other.	
889	What are the unmet needs	2	
890	what are the uniner needs		
801	Emotion	Needs	
802	Elliotion Helplessness fear	Neeus Safaty comfort to everyon and's feelings, recognition	
092 902		Becognition to express one's feelings, recognition	
093	Reipiessness, anger	Recognition, to express one's reelings, safety	
094	Grieve	Safety, comfort, to express one's reelings, recognition	
893	Guilt	Reassurance, reattribution, blaming the correct person	
890	Sname	idem.	
89/			
898	Instruments		
899	- IES-R (Self-reported PTSD-symptoms)		
900	- Caps		
901			
902	4. Study population		
903			
904	4.1 population		
905	Adult patients with a prima	rry diagnosis of PTSD due to trauma(s) that took place before the age of 16	
906	and participate in the IREN	trial.	
907			
908	4.2 Inclusion criteria		
909	See RCT study protocol		
910			
911	4.3 Exclusion criteria		
912	See RCT study protocol.		
913			
914	4.4 Sample size calculation		
915	Will be based on a power a	nalysis not yet completed.	
916			
917	5. treatment		
918			
919	5.1 Investigational treatme	ent	
920	See RCT study protocol.		
921			
922	5.2 Use of co-intervention		
923	See RCT study protocol.		
924			
925	5.3 Escape medication/tre	atment	
926	See RCT study protocol.		
927			
928	5.4 Further treatment		
929	See RCT study protocol.		
930			
931	6. Outcome		
932			
933	6.1 Main study parameter	/endpoint	
934	This will be a qualitative stu	udy using MAXQDA, a computer program for qualitative data analysis.	
935		, , , , , , , , , , , , , , , , , , , ,	
936	6.2 Secondary study paran	neters	
937	N.A.		
938			
939	6.3 Randomisation, blindir	ng and treatment allocation	

- 940 See RCT study protocol
- 941

942 **6.4 Study procedures**

943 See RCT study protocol.944

945 **7. Statistical analysis**

946 This will be a qualitative study using MAXQDA, a computer program for qualitative data analysis. 947

948 8. Adjacent study

949 N.A.

950

951 **9.** Dissemination and Implementation.

- 952 The results of this substudy will be processed in a scientific article.
- 953 Presentations to enlarge the expertise of the participating therapists and other clinicians. Findings
- 954 will be used to adapt existing ImRs treatment protocols.
- 955

956 **10. Time schedule**

957 See RCT study protocol. 958

959 **11. References**

- 960 Arntz, A. (2012). Imagery rescripting as a therapeutic technique; Review of clinical trials, basic
- 961 studies, and research agenda. *Journal of Experimental Psychopathology*. 3, 189-208.

- 964 Oxford, UK: Oxford University Press.
- 965
